Note: Confinement is not required for patients with an implantable cardioverter defibrillator (ICD): Patients with an ICD may reside for some or all of the period from Day 1 to Day 12 in close proximity to the Clinical Testing Unit, eg, at a hotel, provided they can return for all study drug dosing and all study assessments, including but not limited to all serial PK and TTEs. Alternatively, patients may be visited by a home health nurse for selected study drug administration and for any assessments that can be performed away from the clinical site.

Each patient will initially receive placebo BID for 2 days (Days 1-2) in single-blinded manner (“run-in” during acclimatization to confinement in the Clinical Testing Unit) prior to receiving the randomized DB study drug treatment on Day 3. All patients will then receive either placebo or active MYK-491 for 7 days (Days 3-9). More than one patient can be dosed in a cohort at the same time or during the same week depending on administrative issues, i.e., capacity and scheduling.

Patients will be dosed twice daily (every 12 hours). Doses may occur \pm 2 hours from scheduled dosing times as long as doses are separated by at least 10 hours and by no more than 14 hours. The exception to the twice daily dosing is on Day 9 (last dose of randomized DB study drug treatment). On Day 9, a single morning dose will be administered followed by 72 hours of PK and PD assessments.

Before each dosing event, all available safety data from the previous days will be reviewed (for non-confined patients, if a home health nurse is utilized, the nurse and site will be in daily communication to ensure safety). Dosing of DB treatment will take place at approximately the same time each day.

A full PK profile and multiple TTEs and ECGs will be obtained on Days 3 and 9 (corresponding to first and last day of DB treatment respectively) before and after the morning dose. In case of premature permanent treatment discontinuation, perform end-of-treatment visit (same assessments as Day 9) as close as possible to last DB dose (ie, on day of last dose or next day).

Patients will return for a Follow-up visit 7 days following the last dose of study drug. In case of premature permanent treatment discontinuation, perform end-of-treatment visit (same assessments as Day 9) as close as possible to last DB dose (ie, on day of last dose or next day).

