Patients will be dosed twice daily (every 12 hours). Doses may occur ± 2 hours from scheduled dosing times as long as doses are separated by at least 10 hours and by no more than 14 hours. The exception to the twice daily dosing is on Day 9 (last dose of randomized DB study drug treatment). On Day 9, a single morning dose will be administered followed by 72 hours of PK and PD assessments.

Before each dosing event, all available safety data from the previous days will be reviewed (for non-confined patients, if a home health nurse is utilized, the nurse and site will be in daily communication to ensure safety). Dosing of DB treatment will take place at approximately the same time each day.

[figure not shown]
A full PK profile and multiple TTEs and ECGs will be obtained on Days 3 and 9 (corresponding to first and last day of DB treatment respectively) before and after the morning dose.

Patients will return for a Follow-up visit 7 days following the last dose of study drug. In case of premature permanent treatment discontinuation, end-of-treatment visit (same assessments as Day 9) will be performed as close as possible to last DB dose (ie, as best as possible on day of last dose or next day). This visit should include (but is not limited to) the following assessments: TTE, PK, 12-lead ECG, safety labs, troponin and adverse events.

Note: Screening may continue during planned and unplanned SRC meetings. The protocol-specified Screening window may be extended to account for delays due to SRC meetings.

Recommendations by the SRC will include, but not be limited to: (a) evaluation of dose-modification and dose-stopping criteria; (b) doses to be given in specified cohorts; (c) size of specified cohorts; and (d) modification of the number and timing of PK and PD assessments (see [Section 4.4.1](#)).

Figure 1 Study Schema

BID, twice daily; MAD, multiple-ascending doses; PLBO, placebo; QD, once daily; R, randomization; SAD, single-ascending doses; SRC, Safety Review Committee; TBD, to be determined (Period D is optional, based on SRC evaluation).

NOTE: Additional Cohorts D and E, and possible additional cohorts, may be enrolled, eg to explore QD dosing or an alternative BID regimen.

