9 STUDY ASSESSMENTS AND PROCEDURES

The investigator is responsible for ensuring that all staff involved in the study are familiar and comply with the content of this section.

Procedures to be performed during the study are detailed in [Appendix 1](#) and [Appendix 2](#) of this document. Refer to the appropriate schedule(s) of assessments, as indicated in [Table 1](#).

Table 1 Schedules of Assessments

Study Part	Table
Part 1 (SAD): Screening, Dosing Periods, and Follow up – High-Level	Table 2
Part 1 (SAD): Dosing Periods and Follow up – Detailed	Table 3
Part 1 (SAD): Split Dose Screening, Dosing Periods, and Follow up – Detailed	Table 4
Part 2 (MAD): Screening, Dosing Periods, and Follow up – High-Level	Table 5
Part 2 (MAD): Dosing Periods and Follow up – Detailed for Days 3 and 9	Table 6

MAD, multiple-ascending dose; SAD, single-ascending dose

The timelines in [Appendix 1](#) and [Appendix 2](#) should be followed by patients enrolled in Cohort 1 and Cohort A, respectively. Subsequently, the SRC will review all available data. The committee may modify the timing of the assessments or increase or decrease the number of assessments, based on the accumulating data.

Screening values and assessments will be made by the Central Laboratory/reader; in Part 1 (SAD), Day -1 assessments will be split with one sample assayed locally for review by the investigator and one sample assayed centrally.

When several assessments are to be conducted at the same timepoint, the preferred order of assessments is ECG, vital signs, PK, and then TTE. The order of assessments may vary slightly at specific timepoints (eg, 1 hour postdose) to facilitate the most contemporaneous performance of the required assessments. Unscheduled or additional safety assessments may be performed if necessary in the opinion of the investigator.

For assessments that require the patients to be in a semirecumbent or supine position, assessments should be conducted with the patient in the same position at all timepoints.

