9.2 Pharmacodynamic Assessments

9.2.1 *Transthoracic Echocardiography*

TTE evaluations of LVSV (derived from LVOT-VTI), LVEF, LVFS, SET, and other parameters will be PD assessments at the timepoints indicated in [Appendix 1](#) and [Appendix 2](#) (with a window of \pm 1 hour). The patients should be at bed rest for 10 minutes before the

TTEs are obtained. The actual timing of TTE should be modified and/or additional TTEs obtained at other timepoints based on the review of data from prior treatment periods by the SRC. In Part 2 (MAD), TTEs are usually obtained before the morning dose and/or at 7 hours postdose (ie, close to the anticipated peak effect based on the PK profile from the healthy volunteer studies). Up to an additional 2 observations may be requested per treatment period by the SRC after review of the data from previous treatment periods.

Echocardiograms will be evaluated locally for changes that might affect dosing decisions for subsequent doses in one patient or others in the cohort, but the official reading will be done centrally by experts in a core laboratory in a blinded manner with results provided to the SRC.

The sonographers to be used in the study will complete echo protocol training and submit an example of a study to the core laboratory for evaluation. The core TTE lab will certify that the sonographer is able to perform the TTEs at a level satisfactory for obtaining the required protocol data. All echocardiography data will be sent to a central imaging laboratory.

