At Screening and admission, a complete physical examination will be conducted including a neurological examination (gross motor and deep tendon reflexes), and assessment of the following: general appearance, skin, head and neck, mouth, lymph nodes, thyroid, abdomen, musculoskeletal, cardiovascular, neurological, and respiratory systems. At all other timepoints, an abbreviated physical examination (pulmonary, cardiac, abdominal, and other systems related to symptoms) will be conducted.

9.4.4 *Systolic Ejection Time*

See [Section 9.2](#) for a description of assessment of SET using TTE.

9.4.5 *Electrocardiograms (12-Lead ECG)*

The 12-lead ECG should be obtained as indicated in [Appendix 1](#) and [Appendix 2](#). The actual timing of the ECGs may be modified and/or up to an additional 2 ECGs per treatment period may be requested by the SRC after review of the data from previous patients or treatment periods. In addition, the investigator may add extra 12-lead ECG assessments if there are any abnormal findings or if the investigator considers it is required for any other safety reason. If the patient has a new troponin abnormality (see [Section 9.4.9](#)) or any signs or symptoms suggestive of possible cardiac ischemia, additional ECGs should be obtained. These assessments should be recorded as unscheduled assessments. All ECG data will be sent to a central cardiac laboratory.

The investigator will judge the overall interpretation as (a) normal, (b) abnormal without clinical significance, or (c) abnormal with clinical significance. If clinically significant, the abnormality will be recorded. In addition, before each treatment period, the investigator or subinvestigator should review the available ECGs from the previous treatment periods looking for signs of ischemia. If there are signs of ischemia, continued dosing should be withheld until there is full understanding of the possible ischemic changes. Only the overall evaluation (normal/abnormal) will be recorded in the eCRF. The investigator will review the ECG and correlate abnormal findings with any other clinical findings, patient's medical history, and laboratory data to determine the clinical importance of the finding.

The 12-lead ECG abnormalities suggestive of ischemia (eg, new or worsened ST depression or new T-wave inversions), as determined by investigator, will be reviewed centrally by an Adjudication Committee.

9.4.6 *Electrocardiogram Telemetry*

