Plasma [REDACTED] concentration data for MYK-491 will be summarized using descriptive statistics, including mean or geometric mean as appropriate, SD, median, minimum, and maximum values and CV%. PK parameters will include (but are not limited to) C_{max} , T_{max} , AUC, apparent first-order terminal elimination rate constant (λ_z), and MRT. In addition, the accumulation ratios will be calculated with C_{max} and AUC_{0-t} (t = dose interval or τ) after dose on Day 9 (at steady-state) and Day 3 (1st dose). Additionally, the apparent terminal-phase elimination half-life ($t_{1/2z}$) will be calculated.

[REDACTED]

[REDACTED]

11.3.6 *Pharmacodynamic Analyses*

TTE data for LVEF, SET, LVFS, LHSV will be analyzed using descriptive statistics. No inferential analysis will be performed. Observations by timepoint and change from Baseline (either absolute or percent relative change) at each timepoint will be summarized by treatment period (Part 1) and treatment group (Part 2). Change from Baseline will be analyzed with attention to the relationship to time postdose, dose level, and comparison with placebo. For SAD Cohorts, placebo-adjusted change from Baseline will be calculated for each subject at each postbaseline timepoint and then summarized at each dose level. In addition, for SAD and MAD Cohorts, least square means of placebo-adjusted change from Baseline for the key PD parameters (LVEF, LVFS, LHSV, SET) at each postbaseline time point at each dose level may be estimated using mixed model.

The relationship between the TTE endpoints and MYK-491 plasma concentration will be assessed using linear or nonlinear correlations.

11.3.7 *Safety Analyses*

All safety analyses except SET as determined by TTE will be performed on the Safety Analysis population. Analyses of SET as determined by TTE will be performed on the PD Analysis population.

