ⁿ Triplicate 12-lead ECG evaluations will be performed in the supine position after 10 minutes of rest at Screening and at Follow-up visit. See detailed schedule for Days 3 and 9. On Day 2, ECGs should be taken prior to the morning dose. On Day 4 ECG should be taken 7 hours post morning dose. On Day 7 (± 1 day) ECGs should be taken prior to morning dose. On Day 10, ECG is 24 hours post final dose and on Day 11 ECG is post 48 hours final dose. All predose ECGs should be taken within 2 hours of dose, and all other ECGs should be taken plus or minus 2 hours of time point indicated. The investigator may add extra 12-lead ECG safety assessments if there are any abnormal findings or if the investigator considers it required for any other safety reason. If the patient has any signs or symptoms suggestive of possible cardiac ischemia, additional ECGs should be obtained. These assessments should be recorded as unscheduled assessments. For all patients, ECGs will be performed at the study site.

^o ICD download to be performed unless site encounters significant technical difficulties and is required in case of shock(s) delivered by the ICD during the study.

^p Blood sample for HIV, HCV, and HBV will be collected at Screening.

^q Pregnancy tests, urine or blood based on the policy of the local institution or regulating Health Authority (eg, requirement for serum-based testing in the UK), should be performed on all females.

^r FSH tests will be included for potentially postmenopausal women.

- ^s Safety laboratory tests should be split and one sample evaluated by local lab and the other sent to Central Lab. Samples will be taken on days indicated prior to morning dose (except on Day 4, where labs will be taken at 7 hours post-dose). Day 2 local lab results must be evaluated prior to dosing on Day 3. If needed to accommodate local laboratory time tables, Day 2 samples may be taken on Day 1. Safety laboratory tests may be added at the discretion of the investigator. NOTE: Day 7 safety laboratory assessments can be performed ± 1 day if the assessments would fall on a weekend.

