AE, adverse event; BP, blood pressure; CRF, case report form; ECG, electrocardiogram; HR, heart rate; ICD, implantable cardioverter defibrillator; IMP, investigational medicinal product; PK, pharmacokinetic; SAE, serious adverse event; SRC, Safety Review Committee; TTE, transthoracic echocardiography.

^a All predose assessments should be performed within 2 hours of administering the oral dose of MYK-491 or placebo, with the following exceptions: predose or trough PK blood samples should be taken within 1 hour predose, and ECG telemetry monitoring should be initiated at least 1 hour prior to the first dose.

^b Vital signs include temperature, HR, and BP after resting for at least 5 minutes. On Day 9, in the morning (predose), HR and BP should be taken once in the supine position, once after 2 minutes standing, once after 5 minutes standing. All other HR and BP measurements should be the mean of 3 measurements taken in supine position, and BP should be taken via an automated recorder.

^c Triplicate 12-lead ECG evaluations will be performed in the supine position after 10 minutes of rest at Screening, predose, and at 7 hours postdose. The predose ECG on Day 1 should be performed within 2 hours of dosing. The investigator may add extra 12-lead ECG safety assessments if there are any abnormal findings or if the investigator considers it required for any other safety reason. If the patient has any signs or symptoms suggestive of possible cardiac ischemia, additional ECGs should be obtained. These assessments should be recorded as unscheduled assessments. For all patients, ECGs will be performed at the study site.

[figure not shown]
^d Samples for troponin should be split with one sample assayed locally in order to be locally reviewed by the investigator. The other sample will be analyzed at a Central Laboratory. Results of troponin from local lab should guide patient evaluation. Abnormal and/or rising troponin values (as per investigator's judgment and taking into account potential Baseline troponin elevation) should lead to patient being clinically evaluated for possible myocardial ischemia.

[figure not shown]

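### Part 2 text promises an ECG after the Day 9 dose, but Tables 5 and 6 schedule only a predose one, so no planned QTcF reading falls near peak on the steady-state day

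*Combined protocol and SAP*

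**What the plan says.** **Text.** Section 4.1.2 states that "multiple TTEs and ECGs will be obtained on Days 3 and 9 (corresponding to first and last day of DB treatment respectively) before and after" each morning dose. The Part 2 design paragraph of the Synopsis repeats this: "ECGs will be obtained on Days 3 and 9 (corresponding to first and last day of DB treatment respectively) before and after the morning dose".

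**Tables.** In Appendix 2, the 12-lead ECG row of Table 5 gives 0 and 7 h on Day 3, 7 h on Day 4, predose on Day 7 (±1 day), 0 h on Day 9, and then 24 h and 48 h after the last dose. Table 6, the detailed schedule for Days 3 and 9, marks the 7 h ECG as applying to Day 3 alone. The Table 5 ECG footnote adds "On Day 4 ECG should be taken 7 hours post morning dose".

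**Table 6 ECG footnote (c).** "Triplicate 12-lead ECG evaluations will be performed in the supine position after 10 minutes of rest at Screening, predose, and at 7 hours postdose". It has no restriction by day, so it conflicts with the cell it annotates.

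**Which governs.** Section 9 tells sites "Refer to the appropriate schedule(s) of assessments, as indicated in" Table 1, and Section 9.4.5 says "The 12-lead ECG should be obtained as indicated in" Appendices 1 and 2.

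**Why 7 h and Day 9 matter.** Section 9.2.1 places Part 2 echocardiograms "at 7 hours postdose (ie, close to the anticipated peak effect based on the PK profile" in healthy volunteers. Section 11.3.5 bases the accumulation ratios on values "after dose on Day 9 (at steady-state) and Day 3 (1st dose"), so Day 9 is the plan's steady-state day. Echocardiogram, vital signs and PK all have a Day 9 7 h reading in Table 6.

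**The concern.** ECG recordings and intervals are listed among the primary safety measures in Section 11.2.1. The QTcF counts above 450, 480 and 500 ms (Section 11.3.7.3.2) rest on postdose ECGs, and the optional concentration-QTc regression (Section 11.3.7.3.4) needs ECGs matched in time to PK samples. If sites follow the tables, both analyses lack a near-peak reading on the day treated as steady state, although the text tells the reader that one exists.

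In Cohorts A to C the Day 9 morning dose is the last, so a Day 9 postdose reading cannot change that patient's dosing. It can still matter. QTcF above 500 ms is an individual stopping criterion (Section 4.2.4), and two patients on active drug meeting such criteria in a cohort trigger an unscheduled SRC review (Section 4.2.5). The reading would also be among the data the SRC uses to set the next cohort (Section 4.4.1). The early-discontinuation visit in Section 4.1.2 is defined by reference to the Day 9 assessments, so it inherits the ambiguity.

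**Working it through.** **1. Passages side by side**

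| Source | Day 3 ECG | Day 9 ECG |
|---|---|---|
| Section 4.1.2 and Synopsis | before and after the dose | before and after the dose |
| Table 5 | 0 and 7 h | 0 h only |
| Table 6, cell | predose and 7 h | predose only |
| Table 6, footnote c | predose and 7 h | predose and 7 h (no day limit) |

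The two tables agree with each other. The text and the footnote do not agree with them. The text promises a postdose reading on Day 9, and only footnote c specifies 7 h and triplicate.

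**2. Counts under the tables**

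- Double-blind doses under BID: Days 3–8 give 6 × 2 = 12, plus 1 on Day 9 = 13. The Day 4 morning dose is the third.
- ECG timepoints after the first double-blind dose: Day 3 7 h, Day 4 7 h, Day 7 predose, Day 9 predose, Day 10 (24 h), Day 11 (48 h), Day 16 follow-up = 7. Two are at 7 h, both by Day 4; none of the remaining 5 is.
- First ECG after the Day 9 dose: 24 h, with the ±2 h window in the Table 5 footnote, so 22 h at the earliest. That is 22 − 7 = 15 h after the 7 h timepoint.
- Day 9 PK samples up to 12 h postdose: 1, 2, 3, 4, 5, 6, 7, 9 and 12 h = 9, none with a scheduled ECG.
- Planned PK–ECG pairs left for a concentration-QTc analysis: Day 3 7 h, Day 4 7 h, Day 7 predose, Day 9 predose, and 24 h and 48 h after the last dose.

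**3. How much exposure goes unobserved (assumed model)**

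The available text gives neither half-life nor Tmax, so both are assumptions. I used one-compartment superposition with a 12 h interval, half-life *h* from 8 to 24 h in 0.1 h steps, and either bolus input or first-order absorption with Tmax from 2 to 7 h. Concentrations are relative to 7 h after dose 13.

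For bolus input, with r = 2^(−12/h):

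- Day 4 7 h: (1 − r³)/(1 − r¹³)
- Day 9 predose: 2^(−5/h) × (1 − r¹²)/(1 − r¹³)

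| Half-life | Day 4 7 h (bolus) | Day 9 predose (bolus) | Highest at any planned ECG, all input models |
|---|---|---|---|
| 8 h | 0.956 | 0.648 | 0.939–0.956 |
| 12 h | 0.875 | 0.749 | 0.861–0.875 |
| 15.5 h | 0.801 | 0.799 | 0.801–0.836 |
| 24 h | 0.654 | 0.862 | 0.862–0.877 |

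Example at 12 h: r = 0.5, so Day 4 7 h = (1 − 0.125)/(1 − 0.5¹³) = 0.875.

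Coverage is not monotone in half-life. For bolus input, Day 4 7 h is the higher reading below about 15.5 h and Day 9 predose above it, so coverage is lowest where they cross: 0.800 near 15.6 h (bolus or Tmax 2–3 h), rising to 0.824 near 13.8 h with Tmax 7 h. Over the whole grid it runs from 0.800 to 0.956, which leaves about 4–20% of the Day 9 7 h level above any planned ECG.

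**The case against.** The strongest reply is that the tables are deliberate and the loss is small.

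- **Intent.** The Day 3 restriction appears in both the ECG and troponin rows of Table 6, and Table 5 matches it for both. Footnote c also mentions Screening and a Day 1 ECG, neither of which is in Table 6, so it may be carried-over wording. This is plausible. If it is right, the text and the footnote are wrong and still need correcting.
- **Other recordings.** Telemetry runs to about 48 h after the last dose in confined patients, and a 48 h Holter, which Section 11.3.7.4 describes as 12-lead, spans all of Day 8. Neither is a planned source of QTcF. Telemetry needs only three leads and is not required in non-confined patients. The Holter may be set up at any time on Day 7 and comes off 48 h later, so it need not reach 7 h after the Day 9 dose.
- **Part 1.** Triplicate ECGs are taken at 3, 5, 9 and 12 h after 350 mg. With dose-proportional exposure and the model above, the Cohort A (75 mg BID) Day 9 peak is about 35–81% of the highest exposure at a 350 mg ECG. That fits Section 1.3, which predicts that the initial MAD dose reaches exposures already seen in Part 1, and it largely answers the point for Cohort A. The Cohort B and C doses are redacted, so the same check cannot be made there.
- **Benchmark.** The 7 h level is not the modelled peak. It is 55–96% of the Day 9 peak, depending on half-life and Tmax, and Section 9.2.1 ties 7 h to the echocardiographic effect rather than to QTc. This is fair: the 80–96% figure compares with the 7 h timepoint, not with the true maximum. The model also covers BID only, not the optional QD cohorts.
- **SRC discretion.** The SRC may move ECGs or add up to two per treatment period. That is an option, not a plan, and it does not resolve conflicting text.

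There is also no formal hypothesis testing, and the concentration-QTc analysis is optional. These points limit the severity. None supplies a planned QTcF reading after the Day 9 dose.

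**Conclusion.** The concern holds. The text, the tables and the footnote cannot all be followed. If the tables govern, as Sections 9 and 9.4.5 imply, a primary safety measure has no planned 12-lead reading between predose and about 24 h on the steady-state day. That conclusion rests only on reading the schedule.

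The size is moderate. Under the assumed half-lives and Tmax values, planned ECGs already see 80–96% of the Day 9 7 h exposure under BID dosing. The residual concern lies mainly with the cohorts above the initial MAD dose. This should be fixed, but it does not threaten the study.

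**What to change.** Reconcile Section 4.1.2, the Part 2 design paragraph of the Synopsis, Table 5, Table 6 and the Table 6 ECG footnote.

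- **Preferred:** schedule a triplicate 12-lead ECG at the existing Day 9 7 h timepoint in Tables 5 and 6. This delivers the postdose Day 9 ECG that the text already promises. It costs one noninvasive triplicate per patient, at an all-day visit that already has an echocardiogram, vital signs and a PK draw at 7 h, and one cell in each table. Section 4.4.2 already classes an SRC-approved increase in ECGs as a nonsubstantial change.
- **Alternative:** keep the tables, correct Section 4.1.2, the Synopsis and the footnote, and state in the analysis plan and the report that QTcF was not assessed near peak on the steady-state day. This is wording in three places plus the stated limitation. It needs no further data collection but leaves the gap open.
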